Main inclusion/exclusion criteria:	Inclusion: Symptoms of FI, aged over and including 18, capacity to consent, male/female. Exclusion: anal cancer, anal surgery in the last 3 months, acute/painful perianal disease.
Statistical methodology and analysis:	Non-inferiority testing of MAPLe in the assessment of FI will be performed using Bland Altman method. MAPLe will be tested against HRAM and AUS.
	Participants will be grouped according their pathology: Fistula/chronic perianal disease, Obstetric injury <12 months, Obstetric injury >12 months, neuropathic sphincter. Correlation studies and regression analysis to identify which groups benefitted from MAPLe assessment.
	The clinical utilisation of MAPLe will be determined by the outcome of an expert panel.
	Comparative analysis of participant pre and post treatment MAPLe results will identify if targeted treatment has been achieved.

3. Background and Rationale

Burdon of Disease

Faecal incontinence (FI) is defined as the involuntary passage of gas, liquid or solid stool. The symptom is experienced by an estimated 1-10% of the population. FI is associated with a multitude of disease pathologies and prevalent in vulnerable patient groups, the elderly, learning disabilities or severe co-morbidities, and most prevalent in multiparous females. The degree of symptomatic severity is varied and can result in psychological destress and social withdrawal, severely impacting quality of life in up to 22% of suffers(1).

There is significant economic burden associated with FI. Health economic studies have identified US\$4110 as an average annual cost per person, with an increased cost associated with increased symptom severity(2). Further studies estimated a US \$11 billion annual expenditure and a 55% increase in personal cost of health for sufferers(3). Treatment is symptom orientated, further research would improve understanding of the symptom and direct treatment for more effective outcomes.

Anatomy and Physiology of the Pelvic Floor

FI is the result of impairment to the structure or function of the pelvic floor(4). The pelvic floor, levator ani, is a sheet of muscle supporting the weight of the abdominal cavity. It is divided into four muscle groups: pubococcygeus, ilio-coccygeus, coccyges and puborectalis, assisting the maintenance of faecal and urinary continence.

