The role of sEMG in clinical assessment of FI has been limited to research and has not been correlated with current gold standard techniques. This study aims to investigate the sEMG of symptomatic patients using MAPLe. The study will test the non-inferiority of MAPLe against HRAM and AUS in assessing FI. Non-inferiority of a test is defined as the test being no worse than the competitor. The study will aim to identify if particular patient groups have closer correlation

between symptom profiles and FI scores and sEMG results, and whether sEMG improves following treatment. The study will endeavor to identify the clinical utilisation of sEMG in FI.

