3.1 Assessment and Management of Risk

The table below summarise the risks and mitigations of all test above standard care that are being performed in a table:

Intervention	Potential risk	Risk Management
Assessment with MAPLe device	The device will be placed anally and record sEMG, not providing stimulation. As the device will be used in the same nature as current assessment devices no additional risk is perceived.	Performed by trained operator.

4. Objectives

Primary: To determine the role of MAPLe in the assessment of FI in defined patient groups.

Secondary: To determine if targeted treatment is achieved following assessment with MAPLe.

5. Trial design

This is cohort study of participants with symptoms of faecal incontinence. It will take place across two hospital trusts, both able to provide specialist pelvic floor services and facilities required to meet the needs of the study and follow up required by the participants. The use of two sites aims to increase the yield and diversity of participants. The sample size for the study is 120 participants.

Following a stringent selection and recruitment process, participants will be invited to a designated ARP session where they will be consented, complete an incontinence and quality of life questionnaire, and undergo ARP assessment. This will comprise of the current gold standard, AUS and HRAM, and additional assessment with MAPLe using a standardised protocol. Through undertaking all three tests participants will act at their own controls. Participant participation will conclude following ARP assessment unless treatment is deemed necessary by their local MDT. These participants will be followed up at 6 months with interval MAPLe assessment and incontinence and quality of life questionnaire.

The results will undergo statistical analysis to determine non-inferiority of MAPLe in assessing FI. For analysis participants will be allocated to the following groups: fistula/chronic perianal conditions, obstetric injury <12 months, obstetric injury >12months, neurogenic. Each group will be analysed using symptoms profile and MAPLe results to identify correlation. Comparison of MAPle results pre and post treatment will determine if targeted treatment has been achieved.

An expert panel of pelvic floor specialists will be formed to determine the additional benefit of MAPLe in a clinical context. The panel will consist of 3-6 specialists within the field. To reduce bias,

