11.1 Primary Outcome

They primary outcome is to determine which participant groups benefit from assessment with MAPLe. Benefit will be determined by correct identification of abnormalities in symptomatic participants using MAPLe, correlation between symptom profile and MAPLe results, and the outcome of the expert panel. It will be measured once the end of recruitment is reached.

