11.3 Sample size calculation

The sample size has not been formally calculated at this time. This is due to no previous studies on this area being performed. A pilot study to identify the 'normal' measurements for the MAPLe stipulated 30 participants per group to identify a statistically significant result. Accounting for 4 participant groups a sample size of 120 has been set.

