11.5 Statistical analysis

11.5.1 Primary outcome analysis

Non-inferiority testing of MAPLe will be performed using Bland-Altman method. Correlation between MAPLe and AUS for location of sphincter abnormality will be identified. Correlation between MAPLe and HRAM for functional abnormalities will be identified.

Participants will be allocated a patient group dependent on the cause of FI:

- □ Fistula/ chronic perianal conditions
- \Box Obstetric injury <12 months
- \Box Obstetric injury > 12 months
- □ Neuropathic

Each group will be analysed using correlation studies and regression analysis to determine which groups benefit from MAPLe assessment.

The clinical benefit of the addition of MAPLe assessment will be determined from the analysis of the results of the expert panel.

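### Section 11.5.1 judges which of four groups benefit from MAPLe by separate within-group analyses, with no benefit criterion and no comparison between groups, and the 30 per group behind the total of 120 is not secured

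*Combined protocol and SAP*

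**What the plan says.** The primary outcome (section 11.1) is to determine "which participant groups benefit from assessment with MAPLe". Benefit has three parts: correct identification of abnormalities, "correlation between symptom profile and MAPLe results, and the outcome of the expert panel". This point concerns only the correlation part.

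The group-level analysis is described in three places:

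- Section 11.5.1: "Each group will be analysed using correlation studies and regression analysis to determine which groups benefit from MAPLe assessment".
- Section 5 (Trial design): "Each group will be analysed using symptoms profile and MAPLe results to identify correlation".
- Section 2 (Summary, statistical methodology): "Correlation studies and regression analysis to identify which groups benefitted from MAPLe assessment". This wording does not confine the work to one group at a time, but it specifies no model that compares groups.

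The Rationale in section 3 adds a comparative aim: "The study will aim to identify if particular patient groups have closer correlation" between symptoms or FI scores and sEMG.

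On size, section 11.3 states openly that no formal calculation was made. It then takes the number per group from a pilot of normal values, which "stipulated 30 participants per group to identify a statistically significant result", and concludes: "Accounting for 4 participant groups a sample size of 120 has been set".

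The four groups are fistula or chronic perianal conditions, obstetric injury under 12 months, obstetric injury over 12 months, and neuropathic. Inclusion (section 6.1) requires symptoms of FI, not a particular cause. Section 6.3 sets no group quotas, and section 11.4 gives one overall recruitment rate.

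**The concern.** Analysing each group alone yields four correlations and, if they are tested, four separate verdicts. With about 30 patients each, such results scatter widely even when the underlying relationship is identical. If one group crosses a line and another does not, the natural reading is that MAPLe works in the first and not in the second. That inference needs the groups to be compared directly, and no section plans this. Nor does any section say how strong an association must be to count as benefit, so the line itself could be chosen after the results are known.

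The trial could therefore report that MAPLe tracks symptoms in some causes of FI and not in others when nothing differs, as part of its primary conclusion. The sample size adds to this. It is built from a number per group that the recruitment plan does not control, so some groups may be estimated less precisely than section 11.3 suggests.

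**Working it through.** **The plan's own figure.** 4 groups x 30 = 120, which reproduces section 11.3. The 30 itself cannot be re-derived, because no alpha, power, effect size or SD is given.

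**Assumptions.** The documents give no benefit rule, correlations or group shares. For scale only, I assume a two-sided 5% level, the Pearson correlation as the group measure, and the values of r shown.

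**1. Separate verdicts when all groups share the same r.** Under Fisher's z, SE = 1/√(n−3) = 1/√27 at n = 30. The chance p that one group is significant is Φ(atanh(r)·√27 − 1.96) plus the small opposite tail. The chance of a mixed verdict across four groups is 1 − p⁴ − (1−p)⁴.

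| True r, all groups | atanh(r)·√27 | p | Mixed verdict |
|---|---|---|---|
| 0.2 | 1.05 | 0.184 | 0.555 |
| 0.3 | 1.61 | 0.363 | 0.818 |
| 0.4 | 2.20 | 0.595 | 0.848 |
| 0.5 | 2.85 | 0.814 | 0.559 |
| 0.6 | 3.60 | 0.950 | 0.187 |
| 0.7 | 4.51 | 0.995 | 0.022 |

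With no correlation anywhere, at least one group is significant with probability 1 − 0.95⁴ = 0.185.

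A cut-off on the observed r does not remove the problem. With true r = 0.4 in all groups (simulated), cut-offs of 0.2, 0.3, 0.4 and 0.5 give mixed verdicts 39%, 70%, 87% and 71% of the time. With no rule at all, the largest and smallest of the four observed correlations differ by a median of 0.36, 0.31 and 0.24 for a common true r of 0.2, 0.4 and 0.6.

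**2. Precision of one group's correlation.** The 95% CI is tanh(atanh(r) ± 1.96/√(n−3)). For r = 0.4, atanh(r) = 0.424.

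- n = 30: 0.424 ± 0.377, giving 0.05 to 0.66.
- n = 24: 0.424 ± 0.428, giving about 0.00 to 0.69.

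**3. Group sizes.** With 120 in total, all four groups reach 30 only if the split is exactly 30/30/30/30. This needs no assumption. With equal shares and random arrival (assumed), its probability is 120!/(30!⁴ × 4¹²⁰) = 0.0008. The smallest group then averages about 24 (5th to 95th percentile 20 to 28, simulated). With assumed shares of 35/25/25/15% it averages about 18. If 20% of patients fit no group or have unusable data, the mean group size is 120 × 0.8/4 = 24.

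**4. Power of one joint comparison (3 df homogeneity test of correlations).** With one group at r = 0 and three at r, the noncentrality is (n−3) × 0.75 × atanh(r)².

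- n = 30: 3.63 for r = 0.4 and 6.11 for r = 0.5. Simulated power is about 34% and 54%; the noncentral chi-square agrees within about 1 to 2 points.
- n = 24: 2.83 and 4.75. Power is about 26-27% and 42-43% by the two methods.

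**The case against.** The strongest objection is that section 11.1 asks in which groups MAPLe brings benefit, and this needs no between-group test. All four groups could benefit equally, and each could be judged against a preset criterion. That stands, so a reader should not infer that the primary outcome is unanswerable without a comparison between groups. It does not rescue the plan, because no criterion is given. Per-group verdicts also could not support a statement that groups differ, whatever the criterion.

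The closer correlation in the Rationale could be read as closer than existing physiology tests achieve. The sentence speaks of particular patient groups, so a comparison of groups is the more natural reading. Section 11.5.1 specifies neither comparison.

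Regression could include group as a term. Nothing excludes this in section 2, but sections 5 and 11.5.1 describe analysing each group and name no such model.

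A homogeneity test of correlations may look like the obviously safer tool. It is not. If groups share one slope and residual SD but differ in MAPLe spread, their correlations truly differ, and in simulation (30 each, r = 0.4 at SD 1) the test rejects about 25% of the time with one SD doubled and 42% with SDs 0.5/1/1/2. If instead the correlations are equal and the spreads differ, a standard slope-interaction F-test rejects 21-36% of the time in the cases tried. The choice depends on the quantity of interest.

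On size, section 11.3 discloses that there was no formal calculation and does not promise equal groups. Consultant triage (6.3) and review of recruitment figures by the TMG (13.1) offer some oversight, but they are not quotas. A group of 24 rather than 30 widens the interval only modestly.

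**Conclusion.** The point holds in this limited form. The correlation part of the primary outcome has no benefit criterion and no comparison between groups, so differing per-group results could be reported as differences between groups that do not exist. Under an assumed p<0.05 rule and a common true r of 0.2 to 0.5, mixed verdicts occur about 55-85% of the time. The figure falls to 19% at r = 0.6 and 2% at r = 0.7. These rates show scale and do not predict what this trial would report, because the documents set neither the rule nor the correlations.

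Separately, 30 per group is not assured. It would be wrong to infer that 120 is miscalculated, since 4 x 30 is correct. What is missing is any mechanism that delivers 30 to each group, or a place for patients whose cause is mixed or outside the four. Section 3 itself calls the pathogenesis multi-factorial and lists bowel disturbances, which have no obvious home among the groups.

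The data remain usable and the remedy is inexpensive, so this should be corrected but does not undermine the study as a whole. Nothing here bears on abnormality detection or the expert panel.

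**What to change.** 1. **Section 11.5.1, estimates.** Name in advance one MAPLe summary value (manoeuvre, and electrode or muscle grouping) and one symptom score. Report each group's association with its 95% CI, not as significant or non-significant. If a verdict of benefit per group is wanted on this component, write its criterion down beforehand.
2. **Section 11.5.1, comparison.** State that groups differ only on the basis of one joint comparison. Choose in advance either a homogeneity test of correlations or a group-by-MAPLe interaction (slopes, allowing for unequal variances). Say which quantity is compared, because the two can disagree when MAPLe spread differs. Add that a non-significant result is not evidence that groups are alike, and that the joint test does not itself show which groups benefit. State the low power: for one group at r = 0 and three at 0.4-0.5, about 34-54% with 30 each and about 26-43% with 24 each.
3. **Groups.** Add an other/mixed category, reported separately and left out of the group comparison.
4. **Section 11.3.** Restate as: *120 in total; group sizes as they fall; 30 per group not guaranteed.*

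**Cost.** This needs a protocol amendment, approved before it is implemented (section 14), and at most one CRF field. No extra patients or tests are needed. The downsides are that the group comparison is likely to be inconclusive at this size, and that the other/mixed category leaves fewer patients in the four named groups.

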11.5.2 Secondary outcome analysis

To determine if targeted treatment has been achieved participants will be grouped according to the treatment received: biofeedback, neuromodulation, rectal irrigation, and surgery.

Statistical comparison between MAPLe results pre and post treatment for each participant per group will be performed and analysed.

12. Record keeping and archiving

At the end of the trial, all essential documentation will be archived securely by the CI for a minimum of 20 years from the declaration of end of trial.

Essential documents are those which enable both the conduct of the trial and the quality of the data produced to be evaluated and show whether the site complied with all applicable regulatory requirements.

The sponsor will notify sites when trial documentation can be archived. All archived documents must continue to be available for inspection by appropriate authorities upon request.

13. Oversight Committees

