The NHS spends an estimated £100 million on treatment for FI and it is thought patients experience symptoms for 5 years before seeking treatment. If community management of dietary advice, simple anti-diarrhoeal medication and good toileting (17) fail patients are referred to secondary care. Choice of treatment can vary between trusts due to resources and expertise. The treatment options for FI include: medications, biofeedback, rectal irrigation, neuromodulation and other surgical interventions. Patients are referred in a stepwise progressive pattern. This directed by their response to treatment, quantified by FI scores.

Biofeedback is the process of electronically monitoring an autonomic function to acquire voluntary control. Biofeedback treatment for FI has three elements: rectal sensitivity training to improve awareness and response to stool in the rectum, strength training of the pelvic floor using manometric or electromyographic stimulus, or co-ordination training. Biofeedback treatment protocols are varied(18), however 70-80% experience a 50% improvement of symptoms (19). More recent studies have found no significant improvement in symptoms following treatment with biofeedback(20) and biofeedback has been shown to have the same symptom improvement as dietary advice and routine pelvic floor exercises(21).

Rectal irrigation is a treatment for both constipation and FI. The treatment aim is to maintain an empty rectum(22) preventing incontinence episodes(23). Irrigation is performed using a catheter placed in the rectum through which fluid is irrigated resulting in evacuation of the rectum. The treatment has been found to improve symptoms by 44%.

Short title: Assessment of FI with MAPLe

Sponsor code: 119731

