Neuromodulation is a second line treatment for FI in patients with persistent symptoms of FI(24). There are two forms of treatment: sacral nerve stimulation (SNS) and percutaneous tibial nerve stimulation (PTNS). The mode of action is unclear, the treatment applies stimulation to the sacral nerves improving anal sphincter function(25). SNS is an implantable neuromodulator. Prior to implantation, patients undergo a trial period by placement of a temporary wire into the 3rd sacral foramen. If a 50% reduction in symptoms is experienced the patient is offered a permanent implantable device. Studies have shown an 83% continue to have improved symptoms at the 3 years(26). PTNS is a non-implantable form of neuromodulation. The technique was initially developed for the treatment of urinary incontinence; however following reports of improved symptoms of FI further research has been undertaken. NICE references 53% of patients have a good outcome following treatment. However, a recent randomized control trial comparing outcomes following treatment with PTNS vs sham stimulation identified no significant clinical benefit following PTNS treatment(27). Currently PTNS is not recommended for the treatment of FI.

Surgery is performed on the anal sphincter when structural defects are present, most commonly following obstetric injury. The two main surgical techniques used are sphincter repair and sphincteroplasty. Sphincter repair occurs directly after child birth, and is commonly performed by the attending obstetric doctors. Sphincteroplasty is performed by specialist pelvic floor surgeons when large deficits are found on AUS.

Following treatment repeat physiological assessment is not performed as studies have found no improvement(28). Patients who continue to be symptomatic are referred for further treatments.

Rationale

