Studies performed at other centers have investigated the use of surface electrodes (sEMG) on probes(34) placed anally to identify abnormalities or abnormal variants in the innervation and propagation of stimulus within the EAS(35). The anal probes have a series of circumferential sensors that identify the origin and direction of propagation of an action potential. The origin correlates to the

location of an NMJ and innervation zone(19). This technique has been used to investigate asymmetric innervation of the anal canal, particularly important in obstetric medicine(36), but has not progressed from research into clinical utilisation.

The MAPLe device is a new medically certified device distributed by Novuqare using the principals of sEMG in the diagnosis and management of pelvic floor complaints (figure 1).

Figure 1 MAPLe device: anal probe, sEMG detector and charging station.

The probe l has 24 surface electrodes positioned in circumferential bands along its length (figure 2), it is placed in the anal canal. Each sensor detects the sEMG activity in mV for the most proximal muscle fibers (figure 3).

Figure 3 MRI of pelvis with anal probe in situ, confirming correct placement for sEMG detection.

The results are analysed by the receiver to provide numerical values. The values are displayed as a target shaped diagram depicting locational functionality (figure 4 & 5), giving a clear representation of precise areas of weakness in the pelvic floor.

Figure 4 The results can be displayed in three views.

Figure 5 Sensors are grouped together according to the muscle they represent.

The results are displayed on a hand held device in both numerical and diagrammatic formats (figure 6).

Figure 6 Results are displayed on screen in greyscale on target or numerical value.

An independent study tested MAPLe on 229 asymptomatic healthy participants. The study confirmed accurate probe placement to ensure sEMG correlated with correct muscular group, and identified a normal range (27). MAPLe is currently used to provide biofeedback for patients with FI by identifying and targeting muscles with reduced sEMG via visual and electrical stimulation.

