10.4 Data handling

The study is compliant with the requirements of General Data Protection Regulation (2016/679) and the Data Protection Act (2018). All investigators and study site staff will comply with the requirements of the General Data Protection Regulation (2016/679) with regards to the collection, storage, processing and disclosure of personal information, and will uphold the Act's core principles. UCL is the data controller; the UCL Data Protection Officer is [name] [contact]. The data processors are the Student Researcher and the Chief Investigator. The study will be collecting the following data: Age, gender, parity, medical and surgical history, drug history.

Once a participant is enrolled, they will be allocated an individual study number. No record of name/date of birth/address/telephone number will be made. A list of individual study number and associated hospital numbers will be recorded in an encrypted database on a computer within each trust. The list will only comprise of participants recruited from that trust. Data will be provided directly by the participants and recorded on a CRF by the student investigator. Investigation results will be recorded on the CRF. The CRF will not record personal data. The CRF and completed questionnaires will be stored in a locked filing cabinet in the GI physiology department at each trust only accessible to study personnel. The anonymised research data will be collated by the student researcher in an encrypted database on each trust computer. For analysis, a copy of the research data obtained at ASPH will be made and placed on an encrypted USB. This will be transferred to UCLH and combined with the research data from this site. This will be undertaken by the student researcher. The CRF and associated documents will be destroyed 2 years following completion of study by their trust. The electronic database will be stored for 5 years.

11. Statistical Considerations

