Appendix 1 - Schedule of assessments

	Screening (Pre- treatment assessment)	Intervention phase		Final visit	
Visit No:	1	2	3	4	
	Day – X to Day -X	Day 1	Day 7	6 Months	
Window of flexibility for timing of visits:			+/- 7 Days	+/- 14 days	
Informed Consent		Х			
Medical History	Х				
Physical Examination					
Eligibility confirmation	Х	Х			
Faecal incontinence Questionnaire		Х			
Quality of Life Questionnaire	Х				
Anal Ultrasound	UCLH X	ASPH X			
Prescribed History		Х			
HRAM		Х			
MAPLe		Х		If treatment advised x	
MDT			Х		
Adverse Events review	Х	Х	Х	Х	
Concomitant Medication review (if applicable)	Х	Х			

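### Some biofeedback participants may be trained on MAPLe, the device that measures their outcome; section 11.5.2 analyses MAPLe alone, and the schedule records neither treatment received nor device

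*Combined protocol and SAP*

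**What the plan says.** Section 11.5.2 sets the grouping for the secondary analysis: "To determine if targeted treatment has been achieved participants will be grouped according to the treatment received: biofeedback, neuromodulation, rectal irrigation, and surgery". Within each group it compares MAPLe readings before and after treatment. It mentions no questionnaire and does not divide biofeedback by device.

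Section 3 (Background and Rationale) gives MAPLe a second role: "MAPLe is currently used to provide biofeedback for patients with FI by identifying and targeting muscles with reduced sEMG via visual and electrical stimulation". In its treatment overview, the same section lists among the elements of biofeedback "strength training of the pelvic floor using manometric or electromyographic stimulus", and adds that "Biofeedback treatment protocols are varied".

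Other sections bear on the same outcome:

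- Section 11.2 defines targeted treatment by improvement on MAPLe and on incontinence questionnaires.
- Section 5 plans a 6-month visit for treated participants with MAPLe, the incontinence questionnaire and the quality of life questionnaire.
- Section 8.4 makes the offer of treatment the trigger for that visit.
- In Appendix 1 the 6-month column (Visit 4) holds MAPLe, marked "If treatment advised x", and adverse events review. No questionnaire is marked there, and no visit has a row for treatment received, device or sessions.
- Section 10.2 says the data the study needs are all gathered at the physiology session, which comes before treatment.

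**The concern.** Biofeedback that uses an electromyographic signal trains the patient on the kind of signal MAPLe measures. If the training device is MAPLe itself, the pre/post comparison may pick up familiarity with the probe, the display and the squeeze task as well as any change in the muscle. The documents describe no such overlap for neuromodulation, irrigation or surgery.

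An independent measure would limit the damage, and the protocol has one in the St Mark's score (Appendix 3). Section 11.5.2 leaves it out, and the schedule does not collect it when it is needed. Nor does the schedule collect the information that would let an analyst set MAPLe-trained participants apart. At stake is a secondary conclusion, that targeted treatment was achieved with biofeedback, which could rest partly or wholly on a gain specific to the test.

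**Working it through.** **The plan's own figure.** Section 11.3 gives 4 groups × 30 = 120, which reproduces. Those four groups are causes of incontinence, not the treatment groups of section 11.5.2. No section gives the expected number in any treatment group, the SD of MAPLe change, or the size of a training effect.

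**Step 1: can treatment and outcome share a device?** Section 3 states current use of MAPLe for biofeedback. Appendix 5 shows what the MAPLe test asks for: squeezes, an endurance squeeze, pushes and coughs. Section 3.1 says MAPLe only records in this study, but that describes the study assessment, not the treatment a participant later receives. No section names the biofeedback device or rules MAPLe out. Overlap is therefore possible, but not shown.

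**Step 2: would the planned analysis detect it?**

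| Needed | Where it would be | What is there |
|---|---|---|
| Treatment received | Appendix 1, Visit 4 | No row; the MDT entry is at Day 7, before treatment |
| Biofeedback device, sessions | Appendix 1, any visit | No row; concomitant medication review is at Visits 1 and 2 only |
| Incontinence questionnaire after treatment | Appendix 1, Visit 4 | Not marked, although section 5 plans it |
| Analysis of that questionnaire | Section 11.5.2 | Absent, although section 11.2 names it |

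**Step 3: how large could the effect be?** Everything here is an assumption. If a share *s* of the 120 is treated and returns, and treatments divide equally, each group has 120 × *s* / 4 participants: 7.5, 15, 22.5 or 30 for *s* = 25%, 50%, 75% or 100%.

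Take n = 15 and measure the shift *d* in SDs of the paired change. The standard error is 1/√15 = 0.258 SD, so shifts of 0.2 and 0.5 SD are 0.2/0.258 = 0.78 and 0.5/0.258 = 1.94 standard errors. The two-sided 5% critical value on 14 degrees of freedom is 2.14.

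The probability of a significant paired t-test when the only change is the training shift comes from the noncentral t distribution with n − 1 degrees of freedom and noncentrality *d*√n:

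| n | d = 0.2 | d = 0.3 | d = 0.5 |
|---|---|---|---|
| 10 | 9% | 14% | 29% |
| 15 | 11% | 19% | 44% |
| 20 | 14% | 25% | 57% |
| 30 | 19% | 36% | 75% |

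With no shift, each entry would be 5%.

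**The case against.** The strongest reply is that no overlap has been shown. Section 3 describes general use of MAPLe, biofeedback also includes sensory and co-ordination training, and strength training can use a manometric signal. This stands: a reader might infer that participants will be trained on MAPLe, and the documents do not say so. The point is that they leave it open and schedule nothing that would settle it.

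Second, greater activity on squeezing is what strength training aims at, so a MAPLe gain may be real. This also stands. It is a reason to look at symptoms alongside MAPLe, since MAPLe alone cannot tell the two apart.

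Third, treatment may be retrievable. The CRF is not in the documents, and local notes exist at each trust. The list in section 10.4, "The study will be collecting the following data: Age, gender, parity, medical and surgical history, drug history", might be read as proof that treatment is not collected. It is not exhaustive, because the same section adds investigation results. The firmer evidence is Appendix 1 and section 10.2, neither of which provides for data on treatment received.

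Three further inferences go too far:

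- Section 3 says of sacral nerve stimulation: "If a 50% reduction in symptoms is experienced the patient is offered a permanent implantable device". This might be taken to show that offer and receipt differ in this study. It is background on usual practice, and both stages are neuromodulation. What the protocol does show is that follow-up depends on offer while the analysis groups by receipt.
- A reader might suppose that MAPLe gains will be compared between treatments. Section 11.5.2 plans only within-group comparisons.
- A training effect might be thought large enough to settle the biofeedback result. At n = 15 the assumed shifts of 0.2 to 0.5 SD all fall below the critical value, so a significant result from training alone is less likely than not.

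**Conclusion.** The point holds in a limited form. Section 11.5.2 as written would judge biofeedback on MAPLe alone and pool all biofeedback devices, and the schedule contains nothing from which a test-specific gain could be identified. Sections 5 and 11.2 already include the questionnaire, so the analysis and the schedule fall short of the protocol's own definition of the outcome.

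The size of any training effect is unknown. Assuming 15 biofeedback participants, a two-sided 5% paired t-test and a shift of 0.2 to 0.5 SD of the paired change, a significant MAPLe change would arise with probability about 11% to 44% instead of 5%. For 10 to 30 participants the range is 9% to 75%. If no participant is trained on MAPLe or another EMG device, this mechanism does not arise, but the mismatch between sections 5, 11.2, 11.5.2 and Appendix 1 remains.

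This affects a secondary outcome in one treatment group and should be corrected. It does not bear on the primary outcome.

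**What to change.** 1. In Appendix 1 and the CRF, add at Visit 4 the treatment or treatments received, start and end dates, sessions attended and, for biofeedback, whether MAPLe or another EMG device was used.
2. Mark the incontinence and quality of life questionnaires at Visit 4, so that sections 5, 11.2 and 11.5.2 and Appendix 1 agree. Adjust the statement in section 10.2 that all data come from the physiology session.
3. In section 11.5.2, analyse change in St Mark's score alongside MAPLe change in every treatment group. State that targeted treatment will not be concluded for biofeedback from MAPLe change alone. Report MAPLe change separately for participants trained on MAPLe or another EMG device and for other biofeedback participants.

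This changes data capture and analysis only, not the care any participant receives. The cost is a short CRF addition at a visit that already takes place, plus analysis wording. The drawback is smaller biofeedback subgroups for the MAPLe result: if 15 participants divided evenly, the standard error of the mean change would rise from 1/√15 = 0.26 SD to 1/√7.5 = 0.37 SD.
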